## **5.6 Prior and Concomitant Medications and/or Procedures**

Prior therapy is defined as all medications taken by or administered to the patient prior to providing informed consent. Concomitant therapy is defined as all medications taken by or administered to the patient from providing informed consent to the EOS Visit. Review of any concomitant medications should be performed and documented in the source documentation.

### **5.6.1 Excluded Medications and/or Procedures**

The following medications are excluded for the duration of the study. If a patient is taking any of these excluded medications, they must, after signing the ICF, complete a washout consisting of a period of 5 half-lives of the excluded drug 7 days prior to Day 1.

- Oral nonsteroidal anti-inflammatory drugs (NSAIDs).
- Aspirin (>325 mg/day).
- Centrally-acting pain medications (e.g., pregabalin, gabapentin, duloxetine, and/or milnacipran) unless specifically allowed, or allowed with restriction, in the protocol.
- Opioids.
- Topical therapies (e.g., NSAIDs, capsaicin, lidocaine patches, CBD products, or other local treatments) applied to the index shoulder.
- Anesthetic medications injected locally in the index shoulder (other than the selected anesthetic if used for the IA injection procedure).
- Muscle relaxants (e.g., cyclobenzaprine, tetrazepam, and/or diazepam).

The following medications and/or procedures should not be taken and/or performed throughout the study:

- IV or IM corticosteroids within 3 months of the Screening Visit.
- Oral corticosteroids within 1 month of the Screening Visit.
- Inhaled, intranasal, or topical corticosteroids within 2 weeks of the Screening Visit.
- IA corticosteroids in any joint within 3 months of the Screening Visit.
- IA viscosupplementation (hyaluronic acid) or any IA intervention (e.g., IA injection) in the index shoulder within 6 months of the Screening Visit.

- Any investigational drug, biologic, or device within 3 months of the Screening Visit.
- Chemotherapeutic agents, immunomodulators, or immunosuppressants other than corticosteroids within 5 years of the Screening Visit.
- Live or live-attenuated vaccines within 3 months of the Screening Visit.
- Significant changes with regard to physical activity and lifestyle, within 1 month prior to the Screening Visit and changes throughout the duration of the study.

#### 5.6.2 Restricted Medications and/or Procedures

The following medications/nonpharmacologic therapies may be taken or used throughout the study with the following restrictions:

- Aspirin for cardioprotection at a maximum dose of 325 mg/day provided the dose has been stable over the 3 months prior to study entry.
- Medical therapy for depression, including selective serotonin reuptake inhibitors, non-selective serotonin reuptake inhibitors, serotonin and norepinephrine reuptake inhibitors, and tricyclic antidepressants provided the dose has been stable over the 3-month period prior to the Screening Visit (see Appendix E).

#### 5.6.3 Allowed Medications and/or Procedures

The following medications/nonpharmacologic therapies may be taken or used throughout the study:

- Any treatment for a pre-existing condition or for an adverse event, outside of the study indication, that is not listed as excluded or restricted.
- Study-allocated rescue medication.
- Patients should be advised to maintain a stable lifestyle with regard to physical activity throughout the duration of the study. Patients treated for shoulder AC will begin the HEP (see Appendix C) beginning 3 days post injection.

#### 5.6.4 Documentation of Prior and Concomitant Medication Use

During the study, prior medications, changes to concomitant medications, and/or the addition of new medications and the associated reasons for use and/or changes will be documented and recorded on the applicable eCRF.

## **6 STUDY PROCEDURES**

### **6.1 Informed Consent**

Prior to initiation of any study related procedures, patients will review and sign the study's ICF to participate in the study after having been informed about the nature and purpose of the study, participation and termination conditions, and risks and benefits. Patients who are unable to provide informed consent will not be included in the study.

### **6.2 Order of Questionnaires and Electronic Diary Entries**

Entries to be completed daily in the eDiary must follow the order defined in Table 2. Questionnaires to be completed during study site visits must follow the order defined in Table 3.

### **6.3 Screening Visit (Days -21 to -1)**

The study will include a Screening Period of a maximum of 21 days. The following procedures will be performed at the Screening Visit:

- Obtain informed consent.
- Confirm eligibility based on Inclusion and Exclusion Criteria (see Sections 4.1 and 4.2, respectively).
- Complete APR and PRR trainings prior to patient questionnaires.
- Administer the PD-Q, PHQ-9, GAD-7, PCS, and ISI.
- Record medical history, including OA medical history and AC medical history.
  - For glenohumeral OA patients, OA medical history will include American College of Rheumatology diagnosis details; OA diagnosis date (if available); number of days with index shoulder pain in the last month; previous IA corticosteroid, PRP, or hyaluronic injections; presence of OA in other joints; and prior procedures or surgeries for index shoulder OA.
  - For AC patients, AC diagnosis date (if available); pain duration since onset at Screening; previous IA corticosteroid, PRP, or hyaluronic injections; presence of OA in other joints; and prior procedures or surgeries for index shoulder AC.
- Record patient demographics.
- Record prior treatments and medications.
- Record the average daily shoulder pain with movement score (0 to 10 NRS), SI question, and rescue medication usage in the eDiary.
- Record the pain with duration since onset (AC patients only).
- Perform physical examination.
- Perform shoulder assessment, including active and passive ROM, on the index and contralateral shoulder.

- Perform index shoulder X-ray.
  - X-ray of the index shoulder will include axillary view and true anterior-posterior view.
  - For glenohumeral OA patients, the Screening Visit X-ray will be read centrally to confirm Grade 2 or 3 OA in the index glenohumeral joint based on the Samilson-Prieto classification system.
  - For shoulder AC patients, the Screening Visit X-ray will be read centrally to confirm there is no evidence of OA in the index shoulder.
  - An x-ray acquired within 6 weeks of the Screening Visit may be used for study qualification if the specified imaging protocol was followed. The x-ray will be read centrally to confirm there is no evidence of OA in the index shoulder.
- Obtain vital signs.
- Perform ECG.
- Record height and weight and calculate BMI.
- Collect blood samples for hematology and chemistry, including hemoglobin A1c.
- Perform HIV, HBsAg, and HCV screens.
- Perform serum pregnancy test (for women of childbearing potential only). Follicle-stimulating hormone in perimenopausal women who have not had a menstrual period for 1 year will be measured at the Screening Visit.
- Begin washout of excluded medications.
- Register patients in eDiary and provide instructions on its use.
- Dispense rescue medication.
- Assess adverse events and concomitant medications.
- Review HEP video with AC patients to ensure agreement to be compliant.

#### **6.4 Treatment Visit (Day 1)**

The following procedures will be performed at the Treatment Visit (Day 1):

- Confirm eligibility based on Inclusion and Exclusion Criteria (see Sections 4.1 and 4.2, respectively) prior to administration of study medication.
  - Review the average daily shoulder pain with movement (0 to 10 NRS) to ensure at least 5 out of the 7 days prior to Day 1 have been recorded.
- Complete APR and PRR trainings prior to patient questionnaires and administration of study medication.
- Administer the EQ-5D-5L, SPADI, and ASES after completion of APR and PRR training, but prior to any other assessments.
- Review and update medical history prior to administration of study medication.

- Review and update prior treatments and medications prior to administration of study medication.
- Review SI question and rescue medication usage in the eDiary.
- Perform index shoulder assessment including active and passive ROM prior to administration of study medication.
- Obtain vital signs prior to administration of study medication.
- Perform urine pregnancy test prior to administration of study medication (for women of childbearing potential).
- Perform randomization prior to administration of study medication.
- Perform index shoulder aspiration prior to administration of study medication.
- Administer study medication following standard of care procedure.
- Dispense/return rescue medication as needed.
- Assess adverse events and concomitant medications (post injection).
- For shoulder AC patients only, a Home Exercise Program (HEP) will be implemented 3 days following injection and performed twice daily (see Appendix C).

## **6.5 Treatment Evaluation Period (Weeks 1 to 24)**

Following the Treatment Visit, patients will return to the study site for visits that will occur within  $\pm 3$  days of the scheduled time.

### **6.5.1 Weeks 1 to 20**

The following procedures will be performed on Weeks 1, 4, 8, 12, 16, and 20:

- Complete APR and PRR trainings prior to patient questionnaires.
- Administer the EQ-5D-5L, SPADI, and ASES after completion of APR and PRR training, but prior to any other assessments.
- Review the average daily shoulder pain with movement score (0 to 10 NRS), SI question, and rescue medication usage in the eDiary.
- Perform index shoulder assessment including active and passive ROM.
- Obtain vital signs.
- Dispense/return rescue medication as needed.
- Record HEP compliance in the eDiary (AC patients only).
- Administer the PGIC.
- Assess adverse events and concomitant medications.
- For shoulder AC patients only, a Home Exercise Program (HEP) will be implemented 3 days following injection and performed twice daily (see Appendix C).

- 

#### 6.5.2 Week 24 (End of Study Visit)

The following procedures will be performed at the EOS Visit (Week 24):

- Complete APR and PRR trainings prior to patient questionnaires.
- Administer the EQ-5D-5L, SPADI, and ASES after completion of APR and PRR training, but prior to any other assessments.
- Review the average daily shoulder pain with movement score (0 to 10 NRS), SI question, and rescue medication usage in eDiary.
- Perform physical examination.
- Perform index shoulder assessment including active and passive ROM.
- Obtain vital signs.
- Perform ECG.
- Record weight and calculate BMI.
- Collect blood samples for hematology and chemistry.
- Perform urine pregnancy test (for women of childbearing potential).
- Return rescue medication as needed.
- Record HEP compliance in eDiary (AC patients only).
- Administer the PGIC.
- Assess adverse events and concomitant medications.

#### 6.6 Early Termination Visit and Withdrawal Procedures

The end of treatment for patients completing the study is the EOS Visit (Week 24). For patients who withdraw from the study prior to completion (Early Termination [ET]), all EOS Visit procedures will be performed at the corresponding visit. See Section 6.5.2 for the procedures that will be performed.

## 7 EFFICACY ASSESSMENTS

### 7.1 Efficacy Endpoints

#### 7.1.1 Primary Efficacy Endpoint

The primary efficacy endpoint for each of the shoulder conditions (glenohumeral OA and shoulder AC) in this study is the area under the curve (AUC) of the change from Baseline in the weekly mean of the average daily shoulder pain with movement score over 8 weeks for FX006 compared to placebo.

#### 7.1.2 Secondary Efficacy Endpoints

The secondary efficacy endpoints comparing FX006 to placebo for each of the shoulder conditions (glenohumeral OA and shoulder AC) in this study include the following:

- Change from Baseline in the weekly mean of the average daily shoulder pain with movement score at Week 12
- Change from Baseline in the SPADI pain subscale at Week 12
- Change from Baseline in the SPADI disability subscale at Week 12
- The PGIC score at Week 12
- Change from Baseline in the ROM of external rotation at Week 12

#### 7.1.3 Exploratory Efficacy Endpoints

The exploratory efficacy endpoints comparing FX006 to placebo for each of the shoulder conditions (glenohumeral OA and shoulder AC) in this study include the following:

- AUC of change from Baseline in the weekly mean of the average daily shoulder pain with movement score over Weeks 4, 12, 16, 20, and 24
- AUC of change from Baseline in the SPADI pain subscale over Weeks 4, 8, 12, 16, 20, and 24
- AUC of change from Baseline in the SPADI disability subscale over Weeks 4, 8, 12, 16, 20, and 24
- Change from Baseline in the weekly mean of the average daily shoulder pain with movement score at Weeks 1, 4, 8, 16, 20, and 24
- Change from Baseline in the SPADI pain subscale at Weeks 1, 4, 8, 16, 20, and 24
- Change from Baseline in the SPADI disability subscale at Weeks 1, 4, 8, 16, 20, and 24
- Change from Baseline in the SPADI total score at Weeks 1, 4, 8, 12, 16, 20, and 24
- The PGIC score at Weeks 1, 4, 8, 16, 20, and 24
- Change from Baseline in the ROM of external and internal rotation, abduction and flexion at Weeks 4, 8, 16, 20, and 24
- Change from Baseline in the ROM of internal rotation, abduction and flexion at Week 12
- Change from Baseline in the ASES pain subscale at Weeks 1, 4, 8, 12, 16, 20, and 24

- Change from Baseline in the ASES disability subscale at Weeks 1, 4, 8, 12, 16, 20, and 24
- Change from Baseline in the ASES total score at Weeks 1, 4, 8, 12, 16, 20, and 24
- Percent of responders based on the SPADI at Weeks 1, 4, 8, 12, 16, 20, and 24
- Proportion of patients experiencing a  $\geq 20\%$ ,  $\geq 30\%$ , or  $\geq 50\%$  decrease in the weekly mean of the average daily shoulder pain with movement score at Weeks 1, 4, 8, 12, 16, 20, and 24
- Change from Baseline in average weekly rescue medication use
- Change from Baseline in the average weekly SI score
- Change from Baseline in the EQ-5D-5L at Weeks 1, 4, 8, 12, 16, 20, and 24

## 7.2 Efficacy Assessments

Efficacy variables include the following:

### 7.2.1 Shoulder Pain with Movement Score

The average shoulder pain with movement (NRS score) experienced in the previous 24 hours will be recorded daily in the eDiary.

### 7.2.2 Shoulder Pain and Disability Index

The SPADI will be administered at the study visits indicated in Appendix A.

The SPADI will include the pain subscale, disability subscale, and total score.

### 7.2.3 American Shoulder and Elbow Surgeons Standardized Shoulder Assessment Form

The ASES will be administered at the study visits indicated in Appendix A.

The ASES will include subscales for pain, function, and total.

### 7.2.4 Patient Global Impression of Change

The PGIC will be administered at the study visits indicated in Appendix A.

The PGIC will be scored on a 7-point scale.

### 7.2.5 Active and Passive Ranges of Motion

Active and passive ROM will be assessed with a goniometer per standardized measurement protocol, as outlined in Appendix D at the study visits indicated in Appendix A.

### 7.2.6 EuroQol 5 Dimensions 5 Levels Questionnaire

The EQ-5D-5L will be administered at the study visits indicated in Appendix A.

The EQ-5D-5L consists of 2 pages (the EuroQol 5 Dimensions descriptive system and the EuroQol visual analogue scale).

### 7.2.7 Responder Status

Responder status will be defined by:

- Proportion of patients experiencing either a  $\geq 20\%$ ,  $\geq 30\%$ , or  $\geq 50\%$  decrease (improvement) in pain (minimum, at least moderate, and substantial clinically important differences, respectively, as defined by Dworkin et al)

### 7.2.8 Daily Sleep Interference Score

The degree to which index shoulder pain has interfered with sleep during the previous 24 hours will be recorded daily in the eDiary.

## **8 SAFETY ASSESSMENTS**

### **8.1 Adverse Events**

Patients will be monitored for adverse events from the time of informed consent through the end of their participation in the study.

An adverse event is defined as any untoward medical occurrence in a clinical investigation patient administered a pharmaceutical product, which does not necessarily have a causal relationship with this treatment. An adverse event can therefore be any unfavorable and/or unintended sign (including an abnormal laboratory finding), symptom, or disease temporally associated with the use of an investigational medicinal product, whether or not related to the investigational medicinal product.

Patients should be instructed to report any adverse event that they experience to the Investigator, whether or not they think the event is due to study medication. Beginning at the time of informed consent, Investigators should make an assessment for adverse events at each visit and record the event on the appropriate adverse event eCRF.

Wherever possible, a specific disease or syndrome rather than individual associated signs and symptoms should be identified by the Investigator and recorded on the eCRF. However, if an observed or reported sign or symptom is not considered a component of a specific disease or syndrome by the Investigator, it should be recorded as a separate adverse event on the eCRF. For example, a diagnosis of ‘influenza’ should be reported as an adverse event instead of the symptoms of fever, fatigue, malaise, and positive flu test. Additionally, the condition that led to a medical or surgical procedure (e.g., surgery, endoscopy, tooth extraction, or transfusion) should be recorded as an adverse event, not the procedure itself.

Any medical condition already present at the time of informed consent should be recorded as medical history and not be reported as an adverse event unless the medical condition or signs or symptoms present at Baseline changes in severity, frequency, or seriousness at any time during the study. In this case, it should be reported as an adverse event.

Clinically significant abnormal laboratory or other examination findings that are detected or significantly worsen during the study should be reported as adverse events, as described below. The Investigator will exercise his/her medical and scientific judgment in deciding whether an abnormal laboratory finding or other abnormal assessment is clinically significant. Abnormal test results that are determined to be an error should not be reported as an adverse event.

#### **8.1.1 Assessment of Adverse Events by the Investigator**

The Investigator will assess the severity (intensity) of each adverse event and its potential relationship to study medication.

##### Assessment of Severity

Each adverse event should be evaluated for severity or intensity. This is not the same as “serious,” which is based on patient/event outcome or action criteria usually associated with events that pose

a threat to a patient's life or functioning. The severity of adverse events will be assessed according to the following definitions:

- Mild – The adverse event is noticeable to the patient and/or the Investigator but does not interfere with routine activity.
- Moderate – The adverse event interferes with routine activity but responds to symptomatic therapy or rest.
- Severe – The adverse event significantly limits the patient's ability to perform routine activities despite symptomatic therapy.

### Causality Assessment

A medically qualified Investigator must assess the relationship of any adverse events (including SAEs) to the use of the investigational product, as **related** or **not related**, based on clinical judgment and using all available information according to the following definitions:

- Not related – Temporal relationship is lacking (e.g., the event did not occur within a reasonable time frame following administration of the study medication), **or** other causative factors more likely explain the event (e.g., a pre-existing condition or other concomitant treatments).
- Related – There is a positive temporal relationship (e.g., the event occurred within a reasonable time frame following administration of study medication), **and** the adverse event is more likely explained by the investigational product than by another cause (e.g., the adverse event shows a pattern consistent with previous knowledge of the investigational product or the class of the investigational product).

The definition implies a reasonable possibility of a causal relationship between the event and the study medication. This means that there are facts (evidence) or arguments to suggest a causal relationship.

The following factors should also be considered:

- The temporal sequence from study medication administration-  
The event should occur after the study medication is given. The length of time from study medication exposure to event should be evaluated in the clinical context of the event.
- Underlying, concomitant, intercurrent diseases-  
Each report should be evaluated in the context of the natural history and course of the disease being treated and any other disease the patient may have.
- Concomitant drug-  
The other drugs the patient is taking or the treatment the patient receives should be examined to determine whether any of them might be recognized to cause the event in question.
- Known response pattern for this class of study medication-  
Clinical and/or preclinical data may indicate whether a particular response is likely to be a class effect.

- Exposure to physical and/or mental stresses-  
The exposure to stress might induce adverse changes in the recipient and provide a logical and better explanation for the event.
- The pharmacology and PK of the study medication-  
The known pharmacologic properties (absorption, distribution, metabolism, and excretion) of the study medication should be considered.

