### **8.6 Expedited Reporting**

The Sponsor/designee will report all relevant information about Suspected Unexpected Serious Adverse Reactions (SUSAR) that are fatal or life-threatening as soon as possible to the Food and Drug Administration (FDA), and in any case no later than 7 days after knowledge by the Sponsor/designee of such a case. Relevant follow-up information will subsequently be communicated according to the required regulatory timelines.

All other SUSAR will be reported to the FDA as soon as possible but within a maximum of 15 days of first knowledge by the Sponsor/designee.

The Sponsor/designee will also report any additional expedited safety reports required in accordance with the timelines outlined by the FDA.

The Sponsor/designee will also inform all Investigators as required per local regulation.

The requirements above refer to the requirements relating to an investigational medicinal product.

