#### 9.4.2 Analysis of Safety

##### 9.4.2.1 Analysis of adverse events

Safety analyses will be performed on the Safety Population. Adverse events will be coded using the Medical Dictionary for Regulatory Activities (MedDRA). Incidences (number and percent) of treatment-emergent adverse events (TEAEs), those events that start after dosing or worsened in severity after dosing, will be presented by treatment. Incidences of TEAEs will also be presented by maximum severity and relationship to study medication.

Similar presentations will be provided for SAEs, adverse events leading to withdrawal from the study, or adverse events leading to death. Analysis of adverse event data will include examination of the incidence rates of index shoulder-related TEAEs.

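### Section 8.1.1 codes an event as related only if the product is the more likely cause, yet glosses this as a reasonable possibility, so ties fit neither code and plausible but less likely reactions are coded not related

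*Combined protocol and SAP*

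**What the plan says.** The causality rule in Section 8.1.1 begins: "A medically qualified Investigator must assess the relationship of any adverse events (including SAEs) to the use of the investigational product". Only two answers are offered, related and not related.

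- Related needs a positive temporal relationship and, in addition, that "the adverse event is more likely explained by the investigational product than by another cause".
- Not related applies if the temporal relationship is lacking, or if "other causative factors more likely explain the event".

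The paragraph after these bullets states: "The definition implies a reasonable possibility of a causal relationship between the event and the study medication". It explains this as meaning that "there are facts (evidence) or arguments to suggest a causal relationship".

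The code is used in the safety analysis. Section 9.4.2.1 says: "Incidences of TEAEs will also be presented by maximum severity and relationship to study medication". Section 8.6 gives the Sponsor or its designee the expedited reporting of suspected unexpected serious adverse reactions, with a 7-day limit for fatal or life-threatening cases. For the rest: "All other SUSAR will be reported to the FDA as soon as possible but within a maximum of 15 days". Section 8.6 does not define suspected, and does not say whose causality judgement decides it.

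**The concern.** Being the more likely explanation and being a reasonably possible one are different tests. The bullets rank the product against other causes. The sentence after them asks only whether something points to the product. There is no intermediate code to take the events that fall between the two.

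Such events are to be expected here. The Not related bullet gives a pre-existing condition as an example of a competing cause, and every patient enters with index shoulder pain. Section 8.7 itself asks for care in assessing arthralgia in that joint. The trial plans about 35 sites, so two Investigators could each follow the text faithfully and code the same event differently.

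At stake is the meaning of the related rows in the safety tables. Where the bullets are followed, those rows leave out possible reactions for which another cause was thought more likely. Where the explanatory sentence is followed, they include them. A second, smaller matter is which threshold governs once a serious and unexpected case reaches the Sponsor.

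**Working it through.** No arithmetic applies. The check is to apply both wordings of Section 8.1.1 to each judgement an Investigator could reach, and then to follow the result into the sections that use it.

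| Investigator's judgement | Under the two bullets | Under the reasonable-possibility sentence |
|---|---|---|
| A. Timing fits; product more likely than the other cause | Related | Related |
| B. Timing fits; product and other cause equally likely | Neither bullet is met | Related |
| C. Timing fits; other cause more likely, but facts or arguments still point to the product | Not related | Related |
| D. Timing fits; other cause more likely, nothing points to the product | Not related | Not related |
| E. Timing does not fit | Not related | Not related |

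The wordings agree in A, D and E and part in B and C. In B the Investigator must choose between two codes and meets the definition of neither. In C the bullets give a definite answer that the explanatory sentence does not support.

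The downstream sections compare as follows.

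- **Tables by relationship (9.4.2.1).** These depend directly on the code. Events of type C are absent from the related rows if the bullets are followed, and events of type B go either way. If the similar presentations promised for SAEs include the split by relationship, the same holds there.
- **All treatment-emergent events, SAEs, withdrawals and deaths by treatment (9.4.2.1).** Overall incidence by arm does not use the code, so it is unaffected. Index shoulder-related events are also examined in their own right.
- **SAE capture (8.3).** All SAEs are to be entered within 24 hours of awareness, with no causality filter, and the CRO's safety group and the Sponsor's pharmacovigilance group are notified. This is unaffected.
- **Expedited reporting (8.6).** This is a Sponsor or designee task and is not expressly tied to the Investigator's code. Nor does any section set out a Sponsor causality assessment or its threshold. Section 8.2, by contrast, lets the view of either the Investigator or the Sponsor make an event serious.

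**The case against.** The strongest reply is logical. An event more likely explained by the product than by another cause is, by that fact, a reasonable possibility, so the sentence saying the definition implies one need not conflict with the Related bullet. That is right for events coded related, and there is no strict contradiction there. But the implication runs one way only. It does not place a tie, and it does not explain why an event supported by facts or arguments should be called not related because something else is thought likelier. The appeal to clinical judgement and the list of factors to consider do not settle it either: they say what to weigh, not where the line lies.

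The second reply is that the randomized safety comparison does not rest on attribution. That stands in full. The same rule also applies in both arms, and site staff outside the named unblinded roles are blinded, so it lowers the related count in each arm and not for FX006 alone.

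Several stronger readings are tempting, and the documents do not support them.

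- A reader might infer that any event with a competing cause is lost. It is not: if that cause is judged less likely, the event is related.
- A reader might infer that such events escape expedited reporting. The documents do not establish this. Every SAE reaches the Sponsor, Section 8.6 does not bind suspected to the Investigator's code, and Section 5.3 allows the Sponsor's regulatory and pharmacovigilance personnel to be unblinded for safety assessment and reporting. What remains is a risk arising from silence.
- A reader might put the threshold at 50%. The test is comparative and no probability scale is given. Taking each cause separately, with candidate causes at 40%, 30% and 30%, a product at 40% is the most likely explanation. The 50% figure holds only with exactly one competing cause.
- A reader might take hyperglycemia soon after injection in a patient with diabetes as the model case. The Related bullet cites a pattern consistent with the product or its class, and Section 1.3.2 describes glucose elevation after injection, so the rule points toward related. A known effect is also a poor example of an unexpected reaction.

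**Conclusion.** The concern holds in a limited form. Section 8.1.1 has no code for a tie, and it sends plausible but less likely product reactions to not related although its own explanation describes a lower threshold. The related rows in Section 9.4.2.1 can therefore under-count possible reactions and be inconsistent across sites. The number of events cannot be estimated, because the documents give no rates and no indication of how often a competing cause would be judged equal or more likely.

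This rests on three assumptions: that the timing of the event is plausible, that at least some Investigators apply the bullets as written, and that no coding guidance outside these documents already settles the threshold.

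It should be corrected because the rule as written misclassifies some events by the protocol's own stated meaning. It does not threaten the efficacy analyses.

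**What to change.** Reconcile Section 8.1.1 to one threshold, using the meaning the protocol already gives.

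- **Related:** plausible timing and a reasonable possibility, resting on facts or arguments, that the product caused or contributed to the event, even if other causes exist.
- **Not related:** no reasonable possibility. Ties then count as related.
- Remove the more-likely comparison from both bullets.
- State in Sections 8.6 and 9.4.2.1 that this definition applies, and in 8.6 that the judgement of either the Investigator or the Sponsor is enough to make a reaction suspected, in parallel with the rule for seriousness in Section 8.2.

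The cost is about a paragraph of protocol text and matching eCRF guidance. The downside is somewhat more events labelled related in both arms, and possibly a few more expedited reports.
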